3.3 Donor Inclusion and Exclusion Criteria

3.3.1 Donor Inclusion Criteria:

- 3.3.1.1 HLA 6/6 (HLA-A, B, DrB1) related donor or 7/8 (HLA-A, B, C, DrB1) unrelated donor
- 3.3.1.2 Related donors will be evaluated in accordance with HUMC standard practice guidelines for the evaluation and management of allogeneic donors
- 3.3.1.3 Unrelated donors will be identified, evaluated, and managed in accordance with National Marrow Donor Program standards
- 3.3.1.4 KPS of $\geq 70\%$
- 3.3.1.5 Willing to donate bone marrow using standard techniques or peripheral blood HSC by leukapheresis
 - 3.3.1.5.1 Have adequate veins for apheresis or agree to placement of a central venous catheter (femoral, subclavian) if donating peripheral blood HSC

3.3.2 Donor Exclusion Criteria

- 3.3.2.1 Identical twin
- 3.3.2.2 Female donors who are pregnant or breastfeeding
- 3.3.2.3 Infection with HIV or viral hepatitis (B or C)
- 3.3.2.4 Known allergy to filgrastim
- 3.3.2.5 Current serious systemic illness
- 3.3.2.6 Uncontrolled bacterial, viral, or fungal infection
- 3.3.2.7 Receiving experimental therapy or investigational agents
- 3.3.2.8 History of cancer other than treated basal cell cancer of the skin or carcinoma in situ of the cervix. Cancer treated with curative intent >5 yrs before donation will be reviewed on a case-by-case basis by the principal investigator

3.4 Patient Evaluation

Pre-transplant evaluation must be performed within 30 days of transplantation.

- 3.4.1 History with full details of the patient's prior treatments and responses
- 3.4.2 Physical exam with determination of Karnofsky score and findings related to underlying malignancy
- 3.4.3 Chemistry profile to include serum creatinine, AST, alkaline phosphatase, and bilirubin
- 3.4.4 CBC with differential
- 3.4.5 ABO and Rh
- 3.4.6 Serum pregnancy test, if female gender with child-bearing potential
- 3.4.7 HIV, Hepatitis B, Hepatitis C, CMV serology
- 3.4.8 Disease Staging:
 - 3.4.8.1 Bone marrow aspiration and biopsy
 - 3.4.8.2 Morphology
 - 3.4.8.3 Cytogenetic evaluation
 - 3.4.8.4 Fish study for common abnormalities associated with the disease being treated (if previously documented negative, need not be repeated to comply with this requirement).
 - 3.4.8.5 Molecular testing for common abnormalities associated with the disease being treated
- 3.4.9 Pulmonary function tests with DLCO
- 3.4.10 MUGA scan or cardiac echo
- 3.4.11 EKG

3.5 Donor Evaluation

Pre-donation evaluation must be performed in accordance with HUMC Standard Operating Procedures for the evaluation and management of related HSC donors, or with NMDP Standard Operating Procedures for the evaluation and management of unrelated HSC donors.

3.6 HSC Product Evaluation

3.6.1 TNC, CD34+, and CD3+ cell counts

3.6.1.1 Bone marrow or PBSC products may be cryopreserved

3.7 Post-Transplant evaluation

3.7.1 Physical exam daily until hematological recovery and resolution of serious regimen-related complications

3.7.2 History and physical exam weekly through day 100 after transplantation, then at 6 months, 9 months, 12 months after transplantation.

3.7.2.1 Assessment and staging of acute and chronic GvHD will be performed and recorded at these visits and at least weekly through day +100 after transplantation

3.7.2.2 Once weekly assessment of toxicity in accordance with NCI toxicity guidelines from day-1 until resolution of all Grade 3/4 treatment-related toxicities, and then at days +28, +56, +84 (all ± 7 days)

3.7.3 CBC daily from day 0 until ANC $\geq 500/\mu\text{l}$ on two sequential days after nadir reached (engraftment)

3.7.4 Chemistry profile 2 times per week until documentation of engraftment and then weekly through day +100 after transplantation

3.7.5 Chimerism evaluation at days +28, 56, and 84 (± 7 days), at then at 6 months, 9 months, 12 months (± 30 days) after transplantation. The Chimerism assessment will be performed in accordance with the protocol schedule of assessments. If a subject's insurance denies coverage, the assessment may be omitted

3.7.5.1 Peripheral blood samples will be separated to allow assessment of CD3+ cell chimerism

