4.6 Follow-up of Adverse Experiences

- 4.6.1 Patients with Grade 3/4 adverse experiences will be actively followed until the event has subsided (disappeared) or until the condition has stabilized.
- 4.6.2 Adverse events, both serious and non-serious, and deaths that occur during the patient's study participation will be recorded in the source documents. All SAEs should be monitored until they are resolved or are clearly determined to be due to a patient's stable or chronic condition or intercurrent illness(es)

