5.8.6.1 Safety Monitoring Endpoints

The incidence of toxicities of grade 3 or higher toxicities (CTCAE version 3.0), the incidence of probable viral fungal and bacterial infections, and the incidence of treatment-related mortality, i.e., from causes other than relapse or progression, will be recorded for each patient at set intervals over the course of the study. Safety data will be described in a variety of ways, both graphical and tabular, and incidence will be compared across time points and treatment arms. The Data and Safety Monitoring Board will be presented with a comprehensive semi-annual report that will contain both solicited and unsolicited adverse event reports.

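### How often toxicity is graded depends on the patient's own toxicity, which does not fit the fixed-interval comparison planned in 5.8.6.1

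*Combined protocol and SAP*

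**What the plan says.** Section 3.7.2.2 sets the toxicity grading schedule: "Once weekly assessment of toxicity in accordance with NCI toxicity guidelines from day-1 until resolution of all Grade 3/4 treatment-related toxicities". Grading then continues at days +28, +56 and +84, each within 7 days. The section does not say what applies to a patient who never has a Grade 3/4 toxicity, or whether weekly grading resumes after a new one.

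Section 5.8.6.1 covers toxicities of grade 3 or higher, infections and treatment-related mortality. It says these "will be recorded for each patient at set intervals over the course of the study" and that "incidence will be compared across time points and treatment arms".

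Other provisions apply to every patient whatever the toxicity status:
- 3.7.2: "History and physical exam weekly through day 100 after transplantation, then at 6 months, 9 months, 12 months after transplantation".
- 3.7.4: "Chemistry profile 2 times per week until documentation of engraftment and then weekly through day +100 after transplantation".
- 4.6.2: "Adverse events, both serious and non-serious, and deaths that occur during the patient's study participation will be recorded in the source documents".

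Comparing toxicity is the only objective listed in 2.2. Section 5.8.6 presents it descriptively, as incidence rates with 95% confidence intervals, and treats events in the first 100 days as possibly related to the transplant.

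**The concern.** A schedule that changes when a patient's toxicity resolves is not a set interval, so 3.7.2.2 and 5.8.6.1 do not fit together. Two comparisons are exposed.

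The first is across time points. As patients resolve, they move from a grading every 7 days to one every 28 days. Recorded incidence can then fall partly because fewer gradings are made, even if the two arms are identical.

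The second is across arms. If early toxicity lasts longer in one arm, patients there stay on weekly grading longer, and later events are more likely to be found. A difference in duration could then be read partly as a difference in new events. The switch also depends on judging a toxicity treatment-related, and the documents describe no blinding. If toxicities are more readily attributed to treatment in the TBI arm, weekly grading would last longer there even at equal true toxicity. No planned analysis takes account of the number of gradings.

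**Working it through.** The documents give no number of gradings, so there is no stated figure to reproduce.

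**1. Gradings per patient (from 3.7.2.2).** Count every 7 days from day -1 up to the first weekly grading at which all Grade 3/4 treatment-related toxicity has resolved, then add the remaining days among 28, 56 and 84. A fixed day within 3 days after the last weekly grading counts as the same grading.

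| Resolved by day | Gradings to day 84 |
|---|---|
| -1 (no qualifying toxicity) | 4 |
| 20 or 27 | 7 |
| 41 | 9 |
| 55 | 10 |
| 83 or later | 13 |

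The 4 in the first row assumes that weekly grading stops at once in a patient with no Grade 3/4 toxicity, which the section leaves open.

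- Days 29 to 84: weekly gradings fall on days 34, 41, 48, 55, 62, 69, 76 and 83, which is 8. An early resolver has days 56 and 84, which is 2. Ratio 8/2 = 4.0.
- Day -1 to day 84: 13/4 = 3.25 at the extreme, and 13/7 = 1.86 against a patient resolved by day 20.

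**2. Mean gradings per arm.** The documents give no resolution times. These are assumed log-normal with log-SD 0.5, and arm means are simulated.

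| Assumed median resolution day, A vs B | Mean gradings, A vs B | Ratio |
|---|---|---|
| 20 vs 20 | 7.3 vs 7.3 | 1.00 |
| 20 vs 27 | 7.3 vs 8.1 | 1.10 |
| 20 vs 34 | 7.3 vs 8.9 | 1.21 |
| 20 vs 41 | 7.3 vs 9.6 | 1.30 |
| 14 vs 56 | 6.7 vs 10.8 | 1.61 |

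**3. Effect on detection.** As a ceiling, suppose a 7-day event with onset uniform over days 0 to 84 is seen only if present on a grading day. Detection d is 0.514 vs 0.644 (ratio 1.25) for medians 20 vs 34, and 0.459 vs 0.804 (ratio 1.75) for 14 vs 56. With equal medians the ratio is about 1.0.

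This ceiling ignores the weekly visits, chemistry and adverse event recording. If those recover a fraction r of missed events (assumed), detection becomes d + r(1 - d):
- r = 0.5: 0.757 vs 0.822 (ratio 1.09) and 0.730 vs 0.902 (ratio 1.24).
- r = 0.75: 0.879 vs 0.911 (ratio 1.04) and 0.865 vs 0.951 (ratio 1.10).

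**4. In patients.** Take a true incidence of 30% in both arms (assumed), 27 per arm and r = 0.5. For medians 20 vs 34 the recorded rates are 0.30 × 0.757 = 22.7% and 0.30 × 0.822 = 24.7%, a gap of 2.0 points or 0.5 of a patient. For 14 vs 56 they are 21.9% and 27.1%, a gap of 5.2 points or 1.4 patients. The 95% confidence half-width at 30% is 1.96 × √(0.3 × 0.7/27) = 17 points.

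**5. Common weekly schedule through day 100.** Days -1, 6, ..., 97 give 15 gradings for everyone and a ratio of 1.0. The increase is 15 - 7 = 8 for a patient resolving by day 27 or 28, and 15 - 4 = 11 at most.

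**The case against.** A reader might infer that the more toxic arm is graded up to four times as often, and that the arm comparison is biased by construction. The documents support neither. The 4:1 ratio is between two patients at opposite extremes within days 29 to 84. An arm ratio of that size would need every patient in one arm to stay unresolved and every patient in the other to resolve early. Both arms follow the same rule, so if resolution times and relatedness judgements have the same distribution, grading frequency does too.

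The other routes of capture also count. Every patient has a weekly history and physical and at least weekly chemistry to day 100. All adverse events are recorded (4.6.2), 4.3 asks for a CTCAE intensity for each, and 4.4.1.1 reports the maximum grade of listed events rather than a snapshot. A 7-day grade 3 event would normally overlap a weekly visit, so a model with no recovery is implausible. The analysis is descriptive and its intervals are wide. It can also be argued that weekly grading followed by three fixed days is a form of set interval, and that patients still graded weekly have a grading close to each of those days.

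Most of this stands, and it limits the size of the problem. It does not remove it. None of these routes sets a common toxicity grading schedule: 3.7.2.1 requires GvHD to be staged at least weekly through day +100, but nothing comparable is set for toxicity. Chemistry covers laboratory toxicity only. The daily examinations in 3.7.1 also end at a point that depends on the patient's complications. Near-common fixed days would allow a comparison at those days, but 5.8.6.1 does not restrict the comparison to them. The thinning over time remains even when the arms are identical.

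**Conclusion.** The point holds as an ascertainment weakness and an inconsistency between 3.7.2.2 and 5.8.6.1. Grading frequency depends on the patient's own toxicity and on a relatedness judgement. The per-patient extreme is 4:1 between days 29 and 84; arm-level ratios are about 1.0 to 1.6 under assumed resolution times. With half to three quarters of missed events recovered by other routes, the detection ratio is about 1.04 to 1.24 in the unequal scenarios examined. These figures rest on assumed resolution times, event duration and recovery, none of which the documents give.

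The rule may exaggerate a real arm difference, or one produced by unblinded relatedness judgements, and it can make incidence seem to decline over time. The effect is probably modest. The primary endpoint is unaffected. The change is still worth making, because toxicity is the only objective listed in 2.2 and the repair is cheap.

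**What to change.** In 3.7.2.2, grade toxicity once weekly from day -1 through day +100 for every patient in both arms, whatever the toxicity status. The post-transplant gradings can be done at the weekly visits that 3.7.2 already requires. This also settles what applies to patients with no Grade 3/4 toxicity or with a new one, and it matches the 100-day window in 5.8.6. In 5.8.6.1, state that incidence is compared across time points and arms over this common schedule. Follow-up of unresolved events under 4.6.1 is unchanged.

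The cost is a protocol wording change and 15 scheduled gradings per patient: about 8 more for a patient resolving by day 28 and at most 11 more for any patient. No new visits are needed.

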2.2 Secondary Objectives

The secondary objective is to compare the toxicity of each regimen

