3 INVESTIGATIONAL PLAN

3.1 Overall Design and Plan of Study

This is a single institution study of fludarabine and busulfan versus fludarabine, busulfan and low dose total body irradiation in patients undergoing allogeneic stem cell transplantation. A study population of 54 subjects will be enrolled from The John Theurer Cancer Center at Hackensack University Medical Center. Subjects who are eligible to receive allogeneic hematopoietic stem cell transplantation according to the eligibility criteria will be consented and enrolled. Subjects will be randomly assigned to receive one of 2 conditioning regimen: fludarabine and busulfan, or fludarabine busulfan and low dose total body irradiation (TBI). Subjects will be followed until 1 year post transplantation to assess the relapse rate in each arm and transplant-related toxicity

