3.10.1 Conditioning Regimens

Eligible patients who have signed informed consent will be randomized to treatment arm A (Flu-Bu) or treatment arm B (Flu-Bu-TBI).

3.10.2 Treatment arm A:

- 3.10.2.1 Patients must be admitted to HUMC prior to the start of the fludarabine and will not be discharged until engraftment has occurred.
- 3.10.2.2 Fludarabine will be administered at a dose of 40/mg/m² IV daily for 4 days starting on transplant day -6.
- 3.10.2.3 Busulfan will be administered immediately following the fludarabine at a dose of 130 mg/m² IV daily for 4 days starting on transplant day -6.
- 3.10.2.4 Patients will also receive rabbit antithymocyte globulin (Thymoglobulin) at a dose of 0.5 mg/kg IV on day -3, and 1.5 mg/kg on day -2 and 2 mg/kg on day -1
- 3.10.2.5 Hematopoietic cells will be infused on day 0
- 3.10.2.6 Graft versus host disease (GVHD) prophylaxis will consist of tacrolimus 0.03 mg/kg (or 0.015 mg/kg for age \geq 65) using ideal body weight, IV total daily dose starting on transplant day -2 and adjusted based on blood levels. Methotrexate at a dose of 5 mg/m² IV will be administered on transplant days +1, +3, +6 and +11
- 3.10.2.7 Dose adjustment for the fludarabine, busulfan and antithymocyte globulin will be as follows:
 - 3.10.2.7.1 If patient weighs less than 100% of ideal body weight (IBW), dosing is based on actual body weight
 - 3.10.2.7.2 If patient weighs 120-150% of IBW, dosing is based on adjusted body weight (ABW)
 - 3.10.2.7.3 If patient weighs greater than 150% of IBW, actual weight will be capped at 150% of ideal body weight, and this will be used in the adjusted body weight formula
- 3.10.2.8 Corrected body weight formula: ABW= IBW + [(0.25) x (actual BW-IBW)]

3.10.3 Treatment arm B:

- 3.10.3.1 Patients must be admitted to HUMC prior to the start of the fludarabine and will not be discharged until engraftment has occurred.
- 3.10.3.2 Fludarabine will be administered at a dose of 40/mg/m² IV daily for 4 days starting on transplant day -6.
- 3.10.3.3 Busulfan will be administered immediately following the fludarabine at a dose of 130 mg/m² IV daily for 4 days starting on transplant day -6.
- 3.10.3.4 Total body irradiation will be given in 2 fractions of 200 CGY (total 400 CGY) on day -1.

3.10.3.5 All patients in treatment arm B will also receive rabbit antithymocyte globulin (Thymoglobulin) at a dose of 0.5 mg/kg IV on day -3, and 1.5 mg/kg on day -2 and 2 mg/kg on day -1.

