5.8.6 Safety Analysis

Safety Analysis will be performed on all patients who have at least one dose of medication on either treatment arms over the course of this study. The severity of the toxicities will be graded according to the NCI CTCAE v3.0 whenever possible. Events during the first 100 days after transplantation will be considered possibly related to the transplant for this analysis. Regimen-related toxicity will be graded and presented in a descriptive nature as incidence rates and the corresponding 95% confidence intervals.

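### Toxicity is to be followed for 1 year, but the last fixed toxicity-grading visit is day +84 and no attribution rule covers events before day 0 or after day 100

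*Combined protocol and SAP*

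**What the plan says.** Section 2.2 gives one secondary objective: "The secondary objective is to compare the toxicity of each regimen". Section 3.1 sets the horizon: "Subjects will be followed until 1 year post transplantation to assess the relapse rate in each arm and transplant-related toxicity". Section 5.3 also says that patients are monitored for treatment effects for one year from transplantation.

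The only explicit schedule for grading toxicity is section 3.7.2.2: "Once weekly assessment of toxicity in accordance with NCI toxicity guidelines from day-1", continuing "until resolution of all Grade 3/4 treatment-related toxicities, and then at days +28, +56, +84", each fixed visit with a window of 7 days either side. Clinic visits go on longer. Section 3.7.2 requires "History and physical exam weekly through day 100 after transplantation, then at 6 months, 9 months, 12 months after transplantation". GvHD staging (3.7.2.1) is attached to those late visits and chimerism (3.7.5) is scheduled at the same months. Toxicity grading is not.

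Section 5.8.6 says: "Events during the first 100 days after transplantation will be considered possibly related to the transplant for this analysis". It does not say how events before transplantation or after day 100 are attributed. Section 5.8.6.1 records toxicities of grade 3 or higher, infections and treatment-related mortality at set intervals throughout the study, and compares incidence over time and between arms. It does not say what those intervals are.

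**The concern.** The objective and the horizon call for a one-year comparison of toxicity between arms. The data-collection schedule supports a systematic comparison for about the first three months. After that, a newly arising toxicity in a recovered patient is recorded only if someone reports it or notes it at a general history and examination. Incidence built from such reports depends on how carefully each patient happens to be questioned. With a planned 27 patients per arm, a few missed or unevenly captured events could change the picture.

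The start of the window also does not match treatment. In both arms fludarabine and busulfan are given "IV daily for 4 days starting on transplant day -6", whereas scheduled grading starts at day -1 and the 100-day statement starts at transplantation.

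**Working it through.** The plan states no figure on this point, so there is none to reproduce. The check sets the windows side by side and counts days, taking day 0 as transplantation and 1 year as 365 days.

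**Inputs**
- Toxicity horizon: 1 year after transplantation (3.1).
- Last fixed grading visit: day +84, or day +91 at the end of its window (3.7.2.2).
- 100-day attribution statement: day 0 to day +100 (5.8.6).
- Start of conditioning: day -6 in both arms (3.10.2, 3.10.3).
- Start of scheduled grading: day -1 (3.7.2.2). The text is printed in a way that could also be read as day 1.

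**Late side: days remaining = 365 - last covered day**
- From day 84: 365 - 84 = 281; 281/365 = 77%.
- From day 91: 365 - 91 = 274; 274/365 = 75%.
- From day 100: 365 - 100 = 265; 265/365 = 73%.

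The first two figures apply to a patient with no ongoing Grade 3/4 treatment-related toxicity. Where one persists, weekly grading continues with no end date. The order of that clause and the fixed visits is itself unclear, since resolution may come after day +28.

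**Early side**
- Days -6 to -2 inclusive: 5 days of conditioning before scheduled grading (7 days, -6 to 0, if the start is read as day 1).
- All four fludarabine and busulfan doses (days -6 to -3) and the first two of three antithymocyte globulin doses (days -3 and -2) fall in that gap.
- For arm B, section 3.10.3.4 says: "Total body irradiation will be given in 2 fractions of 200 CGY (total 400 CGY) on day -1". On that text, irradiation falls on the first grading day but before the 100-day statement begins. Table 1, as extracted, seems to show irradiation under day 0. If that is not an extraction artefact, the two must be reconciled. On either reading the days -6 to -2 gap comes before irradiation.

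**What else is scheduled late**

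| Assessment | To about day 100 | 6, 9, 12 months |
|---|---|---|
| History and examination (3.7.2) | yes | yes |
| GvHD staging (3.7.2.1) | yes | yes |
| Chimerism (3.7.5) | yes | yes |
| Chemistry (3.7.4) | yes | not listed |
| Toxicity grading (3.7.2.2) | last fixed visit day +84 | not listed |

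**Length of late observation by arm**

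Section 5.9.1 withdraws patients who progress after CR or PR, and adverse-event collection then runs for 28 days. As an illustration, take the design's relapse rates (34% and 13.6%, section 5.4), assume every relapse leads to such a withdrawal, and ignore deaths. Withdrawals by 1 year would then be about 27 × 0.34 = 9.2 in arm A and 27 × 0.136 = 3.7 in arm B. If the treatment works as hoped, arm B is observed for late toxicity longer. Not every relapse will follow a CR or PR, so the real contrast may be smaller.

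**The case against.** The strongest objection is that nothing is left out. Section 4.4.1 applies CTCAE to all toxicities of enrolled patients, and section 4.5.1 asks for causality on each adverse experience without a time limit. Section 4.6.2 records all adverse events and deaths during participation, section 4.2 reports all SAEs, and section 5.8.6.1 plans a study-long comparison by arm. Section 5.8.6 defines the safety population from the first dose.

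This stands against several stronger readings that a reader might make:

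- **Late or conditioning-phase toxicity is excluded from the comparison.** No section says so. The 100-day sentence presumes that early events are possibly related. It does not declare other events unrelated or uncounted.
- **The early gap biases the arms.** Planned treatment on days -6 to -2 is the same in both arms, so the gap mainly understates absolute rates in each.
- **The plan's drug text shows that late harm from irradiation will be missed.** The busulfan section calls lung fibrosis rare and ties it to prolonged treatment, and lists cataract among rare effects. Planned busulfan dosing is the same in both arms, so this says nothing about irradiation. The documents give no late toxicity profile for TBI.
- **The comparison is tilted towards equal toxicity.** No direction is shown. Regimen-related toxicity is also descriptive, with incidence rates and 95% confidence intervals, so no test would declare the regimens equal.

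The objection does not answer the scheduling gap. Recording whatever is reported is not the same as grading every patient at fixed times, and the set intervals of section 5.8.6.1 are defined nowhere beyond section 3.7.2.2. If later grading was always intended, the remedy only writes it down.

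**Conclusion.** The concern holds as a mismatch between a one-year toxicity objective and a grading schedule whose last fixed visit is day +84. About three quarters of the follow-up year (75% to 77%) has no scheduled graded assessment for a patient without ongoing Grade 3/4 toxicity, and 73% lies beyond the 100-day statement. It would be wrong to infer that three quarters of toxicity is missed. How toxicity is spread over the year is not given in the documents.

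The consequence is unsystematic late capture and undefined attribution, so a late difference between arms could be missed or distorted in either direction. Whether such a difference exists is an assumption; the mismatch does not depend on it. The late side matters most for the comparison between arms. The early side affects absolute rates. The change should be made because it alters what is collected and costs little, but the point does not touch the primary analysis.

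**What to change.** 1. In section 3.7.2.2, start CTCAE grading at the first conditioning dose and add it to the existing 6-, 9- and 12-month visits. State how the weekly clause and the fixed visits fit together. Refer to this schedule in section 5.8.6.1 as the set intervals.
2. In section 5.8.6, report regimen-related toxicity by arm from first dose to 1 year, split into up to day 100 and day 101 to 1 year. State how events before day 0 and after day 100 are attributed.
3. For day 101 to 1 year, account for time at risk, because the withdrawal rule in section 5.9.1 can make late follow-up differ by arm. Rates per person-time would serve, as would cumulative incidence with relapse or withdrawal and death handled explicitly. A crude table of percentages would not.

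The cost is one more form page at visits that already take place and one more table. The late period will also bring in some events unrelated to conditioning. Because observation time may differ, these should not be assumed to fall equally in the two arms, which is a further reason for step 3.
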